
I. Objectives

The study has two specific objectives:

- 1- **To identify modifiable health delivery system factors associated with retention in care and sustained virological suppression in HIV-infected women in MCH clinics.** We will use surveys of health facilities, including selected staff, and service beneficiaries (HIV infected mothers) to collect data on key characteristics of the service delivery's organization and providers' and patients' perspective of the HIV care delivery performance. Proportional odds models will be used to identify key modifiable characteristics associated with the main outcomes (LTFU, virological suppression, and MTCT rate).
- 2- **Evaluate the effectiveness of CQI interventions in improving long-term retention in care and virological suppression in HIV-infected women in MCH clinics.** We will conduct a cluster-randomized trial with health districts as the randomization unit. MCH clinics in the

intervention group, will undergo quality improvement initiatives using participatory data-driven approaches and on-site monitoring and supervisory support.

II. Background and Rationale

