Sampling strategy: According to the National AIDS Program, there are a total of 295 MCH clinics in Kinshasa currently providing PMTCT services. To inform selection, study staff will obtain information on factors that might affect the quality of care provided in each facility including: the type of management, location (health district), number of deliveries, number and type of personnel, and onsite HIV pediatric care. This information will be used to stratify clinics. Within each stratum, a random sample of facilities will be taken within each of the 35 health districts in Kinshasa. This selection scheme is adopted to ensure, for example, that health care facilities at the center of the city, which might have lower patient volumes and more patients with higher socio-economic status than facilities in peri-urban areas, are included in the final sample to ensure that the sampled clinics are representative of all clinics of similar size across the province. Clinics will be excluded if less than 500 pregnant women (less than 5 HIV-infected pregnant women) registered for antenatal care (ANC) in the clinic in 2015. All women diagnosed with HIV during pregnancy or breastfeeding in the participating MCH clinics and initiated on ART during the enrollment period and their HIV-exposed infants will be eligible for the study.

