Sample size and Justification: The traditional rule of thumb for sample size in logistic and Cox regression is ten events per predictor.⁷¹⁻⁷³ However, more recent simulation studies have revealed that serious problems aren't experienced until the number drops below five events per predictor.⁷⁴ Given the close association between logistic, Cox, and proportional odds regression models, these studies should provide a reasonable benchmark for sample size determination for our study. Thus, we adopted a rule of seven events per predictor in determining an appropriate sample size. Assuming that 1 contextual-level factor, 2 clinic-level factors, and seven patient-level factors (one socioeconomic, one cognitive, one psychological, one social, one related to accessibility to clinics, and one related to health status) will be significant at the 0.20 level in bivariate proportional odds models and that we'll need five additional terms due to polynomial trends or predictor-by-time interaction effects, our initial models for backward selection will require 105 events. We anticipate that 20% will be lost to follow-up in the first six weeks and 5% will be lost each year thereafter. Thus, for our loss to follow-up model we only require 378 participants.

However, we expect a cumulative MTCT rate of 5% by 24 months that suggests we will need 2,100 participants for this analysis assuming complete follow-up. Accounting for the expected drop-out, we will need to recruit $2100/(0.8*0.95*0.95) = 2,909$ participants. Assuming an average of 10 HIV diagnoses per year at eligible clinics, we will need to enroll in about 105 MCH clinics (3 per districts) in the first three years of the study.

C. Measurement / Instrumentation

Outcomes and measurement: Key programmatic outcomes that will be considered include: loss-to-follow-up (the proportion of HIV+ pregnant women initiated on ART for whom the whereabouts is unknown), retention in care (proportion of participants who are known to be receiving care), non-adherence to scheduled visits (proportion of participants whose whereabouts is unknown or who are in care but have missed at least one scheduled visit over the evaluation period), virological suppression (undetectable viral load), and MTCT rates (proportion of infants born to participating women who are tested positive for HIV).

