We will use a backward selection methodology to build a proportional odds model for each outcome consisting of contextual, clinic-level, and patient-level predictors. Within clinic-level clustering will be accounted for using Generalized Estimating Equations (GEE). Given the large volume of predictors being considered in this aim, we will only include predictors in our initial models for backward selection if significant at the 0.2 level in a bivariate (single predictor) model. At each step of backward selection, variables insignificant at the 0.1 significance level will be removed from the model.

Statistical analyses – Aim 2: The frequencies of outcomes will be compared between the intervention and control groups using adjusted Pearson's Chi-square.⁷⁷ All analyses will be intent-to-treat, meaning that women will be kept in their randomized group independent of whether they actually received (or did not receive) all their care in the group. The intervention and control groups will be compared for baseline prognostic factors and any imbalances that persist after randomization will be adjusted for using logistic regression. Within district- and clinic-level clustering will be accounted for using GEE.

Human subjects' involvement and characteristics

This study will involve HIV-infected pregnant women and their HIV-exposed infants who receive care in one of the maternal and child health clinics providing HIV care in Kinshasa. Clinical record of those participants (mother-infant register) will be accessed by the study team to extract data for the outcomes. In addition those mother will be interviewed on regular basis on sensitive subject

related to their HIV status, social support including relationship with partner. In addition to the discomfort associate with the discussion of such personal topic, there is a potential risk for confidentiality breach associated with the study.

To minimize those risk, all study staff will be retrained on ethical conduct of human subject research. As part of PEPFAR funded routine services for gender-based violence, resource are available at the level of those MCH clinic to provide psychological support for participant who might need them.

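### Aim 2 relies on GEE with about 35 randomised districts but names no small-sample correction or independent cluster; a lesser gap is covariate adjustment triggered by an undefined imbalance

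*Combined protocol and SAP*

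**What the plan says.** The Aim 2 analysis is one short paragraph in Section III.D, Statistical analyses – Aim 2.

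- It opens with the arm comparison ("The frequencies of outcomes will be compared between the intervention and control groups"), made by an adjusted Pearson chi-square that rests on a citation, under intention to treat.
- The arms are then compared on baseline prognostic factors, which are not named, and "any imbalances that persist after randomization will be adjusted for using logistic regression". No criterion for an imbalance is given. The 0.2 and 0.1 significance levels in the same section belong to the Aim 1 model building.
- On clustering there is one sentence: "Within district- and clinic-level clustering will be accounted for using GEE". It gives no working correlation, variance estimator, reference distribution or degrees of freedom, and does not say which level is the independent cluster.

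Section I (Objectives) describes a "cluster-randomized trial with health districts as the randomization unit". Section III.B (Sampling strategy) says that "a random sample of facilities will be taken within each of the 35 health districts in Kinshasa", and the sample size paragraph says that "we will need to enroll in about 105 MCH clinics (3 per districts) in the first three years of the study". The plan does not state the number of districts per arm. The sampling strategy also collects "factors that might affect the quality of care provided in each facility", namely "the type of management, location (health district), number of deliveries, number and type of personnel, and onsite HIV pediatric care". These serve to stratify and sample clinics and are not designated as an Aim 2 adjustment set.

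**The concern.** **Main point.** The sandwich variance used in GEE is justified when there are many independent clusters. In this trial the independent units are the randomised districts, about 35, however many women are enrolled. With so few, the ordinary sandwich variance is on average too small, and a normal reference ignores the uncertainty in estimating it. Intervals come out too narrow and too many null effects are declared significant. The shortfall grows with unequal district sizes and with each district- or clinic-level covariate. GEE also takes one level as independent. The plan names two levels without saying that clinics are nested within the district as the independent cluster.

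**Lesser point.** If covariates enter only when an undefined imbalance is seen, the adjusted model is settled after the arms have been compared. Prognostic factors that happen to balance are then left out. The choice of threshold, and so of model, rests on the analyst.

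Aim 2 is the randomised evaluation of CQI, and the rationale ties scale-up to it, so its error rate and its model should be fixed in advance.

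**Working it through.** **Inputs from the plan (Section III.B), reproduced first**

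- Districts: 105 / 3 = 35. Clinics needed: 2,909 / (10 × 3) = 97, against 35 × 3 = 105.
- Loss to follow-up by 24 months: 1 − 0.8 × 0.95 × 0.95 = 27.8%.
- Recruitment: 2,100 / 0.722 = 2,909, as stated. Women per district: 2,909 / 35 = 83.
- MTCT: 5%.

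**Assumed, because the plan gives no figure:** two-sided 5% test; 17 v 18 districts; ICC 0.01-0.10; district-size CV 0-0.7; independence working correlation; timely infant diagnosis at 40%, the upper bound that the Background gives for testing at 2-3 months.

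**Check by hand (equal district sizes, no covariates, roughly normal district means)**

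1. With m districts in an arm, the sandwich variance is too small on average by (m − 1)/m. Ratio to the true variance: (16/17² + 17/18²) / (1/17 + 1/18) = 0.943; square root 0.971.
2. A normal cut-off of 1.96 then acts like 1.96 × 0.971 = 1.903 on a t scale with 33 df. The two-sided tail is 6.6%.
3. Mancl-DeRouen inflates each residual by m/(m − 1). Variance ratio: (1/16 + 1/17) / (1/17 + 1/18) = 1.061; square root 1.030. With t(33) = 2.035, the effective cut-off is 2.035 × 1.030 = 2.095. The two-sided tail is 4.4%.
4. Interval width, corrected over default: 2.095 / 1.903 = 1.10, so 10% wider.

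**Simulated type I error (logistic GEE, beta-binomial districts, ranges over the assumptions above)**

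| Model | 27.8% and 40% outcomes | MTCT, 5% |
|---|---|---|
| No covariates, default sandwich, normal reference | 6.3%-8.7% | 6.6%-11.0% |
| No covariates, Mancl-DeRouen, t(33) | 4.2%-5.0% | 4.5%-7.0% |
| Three clinic-level covariates, default | 6.8%-9.5% | 7.2%-12.4% |
| Three clinic-level covariates, Mancl-DeRouen, t(30) | 3.7%-4.8% | 4.0%-6.7% |

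A separate run with district-level covariates (ICC 0.01 and 0.05, size CV 0 and 0.6, outcomes 27.8% and 5%) gave, under the default, 6.2%-9.3% with none, 8.2%-11.5% with three and 10.0%-14.0% with six.

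**Imbalance rule**

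The chance that at least one of k independent covariates is flagged at level α is 1 − (1 − α)^k. With k = 3 (assumed; the plan gives no count):

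- p<0.05: 1 − 0.95³ = 14%
- p<0.10: 1 − 0.90³ = 27%
- p<0.20: 1 − 0.80³ = 49%
- Standardised difference 0.25 on district values: its chance SD is √(1/17 + 1/18) = 0.34, so each covariate is flagged with probability 0.46, and 1 − 0.54³ = 84%

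If the threshold is fixed in advance, simulated type I error is 3.1%-5.1%.

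Power was simulated once in the GEE model itself (27.8% outcome, ICC 0.02 and 0.05, covariates acting through the district mean, 3,000 runs per setting, Mancl-DeRouen in both models), where r is the joint correlation of the covariates with the district effect:

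| r | Always adjusting | Never adjusting |
|---|---|---|
| 0.3 | 75% | 75%-76% |
| 0.5 | 77%-81% | 76%-78% |
| 0.7 | 82%-83% | 76% |

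**The case against.** The strongest reply is that nothing in the plan commits to an uncorrected GEE, so no inflation has been shown for the analysis that will be run. That stands: every inflated figure above is conditional. But the sandwich with a normal reference is the ordinary reading of GEE with no further detail, so the silence needs closing.

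Second, the largest figures concern MTCT, which Table 1 lists as secondary, although the Summary counts it among the main outcomes. For Table 1's two primary outcomes the inflation is about 1 to 4 percentage points. The simulations also use 83 recruited women per district; on the 2,100 followed up it would be 60. That changes little: the default gives 6.7%-9.8% for MTCT at ICC up to 0.05.

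Third, a reader might infer more than the documents support:

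- That the imbalance rule inflates type I error. With a threshold fixed in advance it does not. Choosing the most favourable of five thresholds after seeing outcomes would give 6.5%-6.8%, but nothing in the plan suggests that.
- That the rule costs much power. A simpler calculation on district means suggests up to 12 points at r 0.7, but that is not the GEE model, where the gain from always adjusting is about 5-7 points. No document supports any value of r.
- That adjustment could be triggered almost always. A standardised difference of 0.10 would trigger it in about 99% of trials, but that is an extreme threshold when the chance SD is 0.34.
- That the adjusted chi-square is faulty. Its method lies in a citation not available here, and no fault in it has been shown.

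**Conclusion.** The concern holds as two specification gaps of unequal weight.

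The main one is the GEE. With about 35 randomised districts and no stated correction, the usual software default would give type I error of about 6%-9% for loss to follow-up and timely infant diagnosis and about 7%-11% for MTCT, and more with cluster-level covariates. A bias-corrected variance with a t reference brings this to about 4%-5%, or up to about 7% for MTCT at ICC 0.10. These figures rest on the assumed ICC, size variation and 17 v 18 split, and on 35 being the number randomised.

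The lesser one is the imbalance rule. Its fault is that the reported model depends on an undefined threshold and an unnamed set of factors. A fixed list gains about 2 points of power at r 0.5 and 5-7 at r 0.7, under the assumptions of one simulation, and none at r 0.3. At r 0.2 the district-mean calculation shows a cost of up to 2 points.

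This should be corrected, with medium confidence. It does not show that the trial's results will be invalid, and it leaves the stated 2,909 unchanged.

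**What to change.** In Section III.D, Statistical analyses – Aim 2, before outcomes are compared by arm:

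1. State that district is the independent cluster, with clinics nested within it.
2. Specify GEE with independence working correlation, a bias-corrected variance (for example Mancl-DeRouen), and a t reference with df equal to districts minus cluster-level parameters. With intercept, arm and three covariates, each entered as one term, this is 35 − 5 = 30.
3. Replace the imbalance rule with a short list adjusted for whatever the balance, drawn from the clinic factors in Section III.B as recorded before randomisation: for example management type, number of deliveries and onsite paediatric HIV care. State how each is coded. For women enrolled after randomisation, use only woman-level covariates that CQI cannot change, such as age.
4. Say which test is primary. The adjusted chi-square may stay as named if its clustering adjustment is made at district level.

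The cost is SAP wording, clinic data already planned and standard software options. Intervals are 10%-15% wider than default GEE without covariates, and 14%-22% wider with all three, comparing the same adjusted model. Three covariates leave 30 df rather than 33, and if they are weak the adjustment gains nothing or costs a little power. For MTCT, error may still reach about 7% if the ICC is as high as 0.10.

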Appendix.

Specimen collection sheet

Timing	Pregnancy and Delivery		Post partum Period	
Study Visit	Enrollment	Delivery	6 weeks	6, 12, 18, 24 months
Mother's specimen	Blood	Blood	Blood	Blood
	Urine	Urine	Urine	Urine
Infant's specimen		Cord blood	Blood	Blood
		Placenta biopsie
